In addition, we will collect EMA data from 25 participants in each condition to obtain more granular data on the momentary relationship between varenicline use, adverse events, smoking, craving, and mood in the critical first two weeks after medication use begins. Outcomes of greatest interest are the within-person relationships between medication use (e.g., adherence), medication safety (e.g., adverse events), quit rates (self-report and biochemically validated), and factors that are associated with specific treatment outcomes.

Study sites

This study will be implemented at both Los Angeles Clinical Trials (LACT) and the Arizona State University. [name] will implement the study in Los Angeles; [name] will implement the study in Phoenix.

Human Subjects Protection. Western IRB (WIRB) will be the IRB of record for this study, and the ASU IRB will receive the WIRB approvals and maintain documentation because it is the institution that has received funding from NIH. WIRB approval is required for study implementation. WIRB will maintain records for the study, and the ASU IRB will maintain a copy.

Recruitment. We are making changes below due to the COVID-19 pandemic. The COVID-19 pandemic has resulted in a drop in the number of potential participants contacting both sites in response to recruitment advertisements. Due to the lower number of respondents, we would like to increase the geographical area from which we are recruiting. By allowing for

remote participation, we will we recruit nationally in addition to local site recruitment for inperson participation.

There will be two cohorts for this study going forward: one in-person cohort, and one remote cohort. We will recruit both cohorts via paid and free (e.g. Craigslist, Facebook, etc.) advertisements, as we have for other studies. We anticipate, based on previous studies, that we will need to recruit well over 2500 potential participants, of which 700 will be screened before 432 will ultimately be randomized. Fortunately, both sites can draw from large local populations that are demographically diverse.

Participants. We will recruit male and female smokers of any race/ethnicity who are at least 21 years of age (with no upper age limit). Our anticipated recruitment plan is: 60% male, 80% white, 10% black, 7% American Indian/Alaska Native, and 3% Hispanic. No vulnerable populations (eg incarcerated, mentally handicapped, etc) will be included; the specific inclusion/exclusion are below.

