Visit Window. Table 2 shows the target and allowed windows for study visits. Except for Week 2 where the telephone visit should be no more than 2 days on either side of the target visit day, the allowed window for each visit is 5 days before or after the target visit. Visits outside of those ranges are allowed, but must be documented (eg vacation, difficulty contacting, illness, etc).

Table 2. Target and allowed windows for study visits for the In-person and remote cohorts.

Visit Week	Target Day in Relation to Randomization Date	Allowed Window (days)
BL		
2 (call)	14	12-16
4	28	23-33
8	52	47-57
12	98	93-103
13 (call)	105	100-110
26	182	177-187

Inclusion Criteria for the In-person Cohort

- 1. 21 years of age or older
- 2. Self-reported daily smoker
- 3. Breath CO > 10ppm
- 4. Motivated to quit smoking completely within five weeks of the Screening Visit (>5 on reported motivation)
- 5. Capable of and agree to complete study requirements
- 6. Literate in English, self-report

- 7. Must be available for the duration of study
- 8. Informed consent obtained
- 9. Willing and able to provide additional data between visits using ecological momentary assessment (EMA)
- 10. Must own study compatible smart-phone (iPhone or Android)

Exclusion Criteria for the In-person Cohort

- 1. Any self-report, diagnosis or treatment of heart attack, unstable angina, angioedema, seizures, cerebrovascular accident (CVA) within the last six months.
- 2. Any self-report, diagnosis or treatment of bipolar, schizophrenia or suicidal ideation within the last six months. (For suicidal ideation a score of ≥7 on the Suicidal Behavior Questionnaire, see Appendix 15)
- 3. Self-report of diagnosis or treatment for depression within the past six months, unless participant has written permission by their healthcare provider to participate
- 4. Systolic blood pressure 160 or higher and/or diastolic blood pressure 100 or higher (see site applicable SOP for Evaluating and Reporting Blood Pressure and Appendices 5 and 6 for participant handouts)
- 5. History of renal disease
- 6. Allergy to any of the ingredients in varenicline
- 7. Participation in another smoking cessation program or any type of clinical trial in the past 3 months
- 8. Use of any smoking cessation medication in the past three months
- 9. Any other medical condition(s) which the licensed study physician deems unacceptable for participation in this study

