Product will be packaged for each in-person cohort study visit as follows: (1) Baseline to Week 4: During the first week after baseline, when participants start and ramp up their dose, standard multi-compartment pill organizer containers will be provided to study participants with their assigned dosing regimen (as indicated above). In addition, participants will be provided 28 days of their maintenance twice daily dose in a standard child resistant-pill bottle. This will allow for an extra 7 days of IP to account for delays in attending the Week 4 visit. (2) Week 4 and Week 8: Medication will be provided in a pill

bottle at each visit, and in order to assure adequate supply in case of a delay in study visits, each container will contain enough product to last 5 weeks. All containers will be child-resistant for added protection, and labeled appropriately for the study.

Product will be packaged **for the remote cohort** as follows: product will be mailed after the second baseline visit. The first week of starting the medication, when participants start and ramp up their dose, standard 7-day multi-compartment pill organizer containers will be provided to study participants with their assigned dosing regimen (as indicated above). In addition, participants will be provided 12 weeks of their maintenance twice daily dose in a standard child resistant-pill bottle. All containers will be child-resistant for added protection, and labeled appropriately for the study.

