Product Education Information. When participants are provided Investigational Product the first time (Screening/Baseline 1 or 2), they will be given a consumer-friendly handout, Chantix Use and Safety Information (Appendix 12) that includes information on how to use the medication, smoking cessation withdrawal symptoms, side effects and adverse events, and information on smoking cessation quitlines. This handout is a modification of the FDA-approved Chantix Medication Guide (Appendix 14), which was modified to meet needs of the study. The handout will include information on setting a quit date that exists on the Chantix™ website. The recommendation will be to set a quit date for Day 8 of medication use, or up to 30 days after starting the study product. Note that participants in all study conditions will have product available for a maximum of 12 weeks. If participants wish to use the medication beyond 12 weeks, they will need to contact their own health care provider for a prescription that they can fill at their own expense. We will assess at each follow-up visit whether any participants used varenicline beyond the 12 weeks of this study.

Blinding. Our statistician will create the code that will allow identification of which numbered product is varenicline or placebo, and the code will be maintained in a sealed envelope in a locked cabinet by the ASU and LACT study sites that can be readily accessed in case of emergencies.

Medication Cost. There will be no medication cost to participants. Because some of the participants will receive placebo, charging for the product would not be reasonable. In addition, this design is consistent with the approach approved by the FDA when testing NRT OTC studies, so we want to use a design that has potential relevance to the FDA.

Adverse Events

Handling Adverse Events. Multiple very large studies have demonstrated that varenicline has a safety profile that is very similar to NRT⁵. Clinical trials to date indicate that varenicline utilization results in very few serious adverse events. However, we will take tracking and management of adverse events very seriously (as we have in our previous studies). As indicated above, we will make sure to assess adverse events that might reflect exacerbation of any reported or unreported psychiatric disorders.

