participants no more than 90 seconds to complete. To reduce missing data, participants who miss more than two sequential days of evening daily diaries or complete fewer than three scheduled prompts a day for two sequential days will receive encouragement texts and calls from an RA to troubleshoot any problems with the app and encourage compliance.

Definitions of Success

FDA Abstinence Criteria. As indicated earlier, in all studies that assess medications for smoking cessation, the FDA typically requires verification of 28 days of continuous abstinence, i.e.; not a single puff from a single cigarette. The FDA does not require the 'clock' to start at a consistent time point after study enrollment. Thus, in many studies the 'clock' on that 28 days begins two weeks after study medication has begun, while in other studies the 'clock' starts at a different time point. In the current study, we will follow the protocol used in the varenicline pivotal trials. ^{6,17-20} The primary study outcome in the proposed study will be continuous abstinence between weeks 8 and 12 after study medication has begun. Subjects who are randomized but who never obtain medication will be considered treatment failures and will be included in the denominator in the intent-to-treat analyses.

D. DATA SAFETY MONITORING PLAN

Participant Safety. This study includes the use of a medication, varenicline, that is FDA-approved, as well as the same medication at a lower dose than approved by the FDA, in order to assess whether smokers can choose and use the medication without a healthcare provider prescription. Given the existing data, the likelihood of participants experiencing a serious adverse event from the use of varenicline is very low. In fact, in one of the largest smoking cessation studies ever conducted, the adverse events related to varenicline were similar to those from the nicotine patch, which is already approved as an OTC medication.

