2	Did cigarettes taste good?
3	_Did you enjoy the sensations in your throat and chest?
4	_Did smoking calm you down?
5	_Did smoking make you feel more awake?
6	_Did smoking make you feel less irritable?
7	Did smoking help you concentrate?
8	_Did smoking reduce your hunger for food?
9	_Did smoking make you dizzy?
10	_Did smoking make you nauseous?
11	_Did smoking immediately relieve your craving for a cigarette?
12	_Did you enjoy smoking?

Smoking Status and Resource Utilization

Smoking status

At al	l visits

- 1. Did you smoke any cigarettes, even a puff, since your last visit? Yes No
- 2. [If Yes to 1] Did you smoke any cigarettes, even a puff, in the last 7 days?

It has been approximately	weeks since your last visit.
3. On approximately how many days	s did you smoke?
4. On the days that you smoked, wh	at is the average number of cigarettes that you
smoked?	

Resource utilization

At all visits

- a. Since your last visit, which of the following additional things have you tried to reduce or quit smoking? Check all that apply.
- a) A pamphlet or book
- b) Individual or group counseling
- c) Telephone counseling / quitline
- d) Nicotine patch, gum, nasal spray, lozenge, or inhaler
- e) E-cigarettes
- f) Zyban / bupropion
- g) Switching to chewing tobacco or snuff
- h) Switching brands
- i) Cutting back
- j) An Internet quit smoking program
 k) Alternative methods like herbs, lasers, homeopathic medicines, prayer, acupuncture, or hypnosis

 Somet 	hing else:	
---------------------------	------------	--

Medication compliance and perceived efficacy

Medication	efficacy	and com	npliance

Λt	വ	\ / /	101	t-c
Αt	aı	ı v	ı	ເວ

- 5. This medication is helping me/has helped me quit smoking.
- a) Strongly disagree
- b) Somewhat disagree
- c) Neither agree nor disagree

d) Somewhat agree e) Strongly agree f) Don't know
At Week 2 telephone call only a. It has beendays since your last visit. After the first 3 days of taking the study medication the instructions were to take 2 pills per day. Approximately what percentage of days did you take: itwo doses per day iione dose per day iiino doses
At the Week 4, 8 and 12 visits 6. It has been number of days since your last visit.
Approximately what percentage of days did you take:two doses per dayone dose per dayno doses
Ask #7 only if any study product was reported as not used as recommended 7. Main reason for not using medication as recommended (check only one): forgotside effectnot workingdon't needother Specify:

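### Table 2 sets the Week 8, 12 and 13 visits at days 52, 98 and 105, where 7 × week gives 56, 84 and 91, and counts from a different day 0 than the primary endpoint

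*Combined protocol and SAP*

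**What the plan says.** - **Endpoint** (section C, Definitions of Success): "The primary study outcome in the proposed study will be continuous abstinence between weeks 8 and 12 after study medication has begun". The same paragraph cites 28 days without a single puff as the usual FDA standard. The endpoint sentence itself gives no day count.
- **Visit days** (Visit Window, Table 2): the target column is headed "Target Day in Relation to Randomization Date". Targets for Weeks 2, 4, 8, 12, 13 and 26 are days 14, 28, 52, 98, 105 and 182. Windows are ±5 days (±2 at Week 2), and visits outside them are permitted if documented.
- **Remote cohort**: its Visit Window paragraph adopts Table 2. Its Screening/Baseline Visit 2 text bases the remaining visits on the date medication starts, and allows 30 days from the first screening visit to begin it.
- **Smoking status questionnaire**: item 1 asks "Did you smoke any cigarettes, even a puff, since your last visit". If yes, item 2 asks "Did you smoke any cigarettes, even a puff, in the last 7 days". Item 3 ("On approximately how many" days) collects a count without dates.
- **Verification**: Study Design lists "quit rates (self-report and biochemically validated") among the outcomes of greatest interest. Week 12 includes breath CO (in-person) or urine cotinine (remote, if reporting not smoking).
- **Product**: for the in-person Week 4 and Week 8 supplies, "each container will contain enough product to last 5 weeks" (Product Packaging). Under Product Education Information, "participants in all study conditions will have product available for a maximum of 12 weeks".
- **SAP, Main study**: the logistic model takes cessation at 12 weeks as its outcome and names no day window.

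**The concern.** The primary endpoint needs one visit to open the abstinence period and another to close it. In Table 2 both sit on days that disagree with their week labels: the opening visit is four days early and the closing visit fourteen days late. A participant abstinent for the whole of weeks 8 to 12 who smoked just before or just after could then be recorded as a failure, and the chemical test would be taken after the endpoint period had ended. Separately, if Table 2 and the endpoint count from different days, the same visit can fall at a different point in the endpoint period for different participants. At stake is whether the quit rates that the SAP reports with 95% confidence intervals describe the endpoint as defined.

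**Working it through.** **1. Reproduce the table.** Target = 7 × week; window = target ±5 days (±2 at Week 2).

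| Visit | 7 × week | Table 2 target | Difference | Table 2 window | 7 × week inside window? |
|---|---|---|---|---|---|
| Week 2 | 14 | 14 | 0 | 12–16 | yes |
| Week 4 | 28 | 28 | 0 | 23–33 | yes |
| Week 8 | 56 | 52 | −4 | 47–57 | yes |
| Week 12 | 84 | 98 | +14 | 93–103 | no |
| Week 13 | 91 | 105 | +14 | 100–110 | no |
| Week 26 | 182 | 182 | 0 | 177–187 | yes |

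Three rows reproduce exactly and three do not, so no constant offset explains the differences. Each window is centred on its printed target, so an error in reading the PDF is unlikely.

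**2. Interval between the Week 8 and Week 12 visits.**
- Weeks 8 to 12 by label: 84 − 56 = 28 days, which agrees with the cited criterion.
- Table 2 at target: 98 − 52 = 46 days.
- Table 2 in window: shortest 93 − 57 = 36 days, longest 103 − 47 = 56 days. Documented out-of-window visits could fall outside this range.

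If the Week 12 answer to item 1 decides the endpoint, these are the days it covers. At target the excess is 46 − 28 = 18 days. With medication started on day 0, that is 4 days before day 56 and 14 after day 84.

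**3. Timing of the Week 12 test, with medication started on day 0.** 93 − 84 = 9, 98 − 84 = 14 and 103 − 84 = 19, so breath CO or urine cotinine is taken 9 to 19 days after the end of week 12.

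**4. What the last-7-days item can separate.** At the earliest in-window Week 12 visit, seven days back is day 93 − 7 = 86, already past day 84. A yes to item 2 with one day smoked in item 3 therefore places that lapse after day 84. At the target visit, seven days back is day 98 − 7 = 91, so a lapse on days 85–90 cannot be told apart from one on days 56–84. Nor can the form place every lapse when several days were smoked.

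**5. Effect of the day-0 difference.** If medication starts k days after randomization, weeks 8–12 run from day 56 + k to day 84 + k on Table 2's clock. At k = 0 that is days 56–84. At k = 14 it is days 70–98, so the Week 12 target is exactly the end of the period. At k above 14 the target visit comes before the period ends. The results in step 3, the 4 + 14 split in step 2 and the day-84 comparison in step 4 therefore hold only when k is small, or when Table 2's days are counted from medication start.

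**The case against.** The strongest reply is that the documents never say how the endpoint is scored. Scoring from one visit to the next is inferred from item 1 of the questionnaire; Definitions of Success and the SAP are both silent. That stands, so the 46-day interval carries two conditions: Table 2 is followed, and item 1 is used.

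It can also be said that weeks 8 and 12 simply mean the visits so labelled, which would leave only a labelling problem. The missing day count gives this some force. But the endpoint sentence counts from medication start, the paragraph cites 28 days, and product is limited to 12 weeks, so a 46-day interval ending at day 98 still conflicts with the surrounding text.

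A reader might infer more than the documents support:

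- **That every lapse after day 84 is scored as failure.** Step 4 shows that some can be placed after day 84 from existing items.
- **That the measured endpoint is always the stricter one.** Step 5 shows that this fails when medication starts more than 14 days after randomization and visits are not re-anchored.
- **That in-person product runs out.** The 46-day target gap exceeds the 5 × 7 = 35 days in the Week 8 container, but product is limited to 12 weeks. A container given on day 52 reaches about day 52 + 35 = 87, past day 84, so the gap is no measure of a shortfall at target.
- **That treatment comparisons are biased or lose power.** Nothing in the documents gives lapse rates in the extra days, overall or by arm.

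How to score a denial of smoking with a positive or missing test is a separate question.

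**Conclusion.** The point holds in limited form. Without further assumptions, three of the six dated rows in Table 2 disagree with their week labels (−4, +14 and +14 days), day 84 lies outside the Week 12 window, and the table and the endpoint use different starting days. The documents do not show whether the printed days or the labels were intended.

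The effect on the endpoint is conditional. If Table 2 is followed and the Week 12 since-last-visit item decides the outcome, abstinence is scored over 46 days (36–56 in window) instead of 28. If, in addition, medication starts at or near day 0, smoking after week 12 could count as failure, and measured quit rates could be understated against the defined endpoint. The size of that understatement cannot be worked out from the documents. The arithmetic is certain; the scoring route is an inference.

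**What to change.** 1. Reconcile the Table 2 target days and windows for Weeks 8, 12 and 13 with the week labels, the endpoint definition, and the Product Packaging and Product Education Information text. State one day 0 and use it for both cohorts. Cost: three table rows and one sentence.
2. For participants whose Week 8 and Week 12 visits followed the printed days, report the actual visit days and describe the endpoint as abstinence since the Week 8 visit. Cost: a short SAP addition and one descriptive summary. Their scored interval cannot be shortened afterwards.
3. Optional: at Week 12, ask about any puff between the start and end dates of the reconciled endpoint window. Windows of ±5 days vary the recall period whatever the targets. For illustration, targets at 7 × week would still give 79 − 61 = 18 to 89 − 51 = 38 days. Cost: one questionnaire item, which cannot be collected for participants already past Week 12.

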Adverse Event (AE) Definitions. Any negative event subsequent to signing consent but prior to the week 13 visit will be considered a potential adverse event to be addressed and followed, regardless of whether it is related to use of study medication. Examples of AEs include: (1) Clinical signs and symptoms, (2) Abnormal test results, (3) Worsening of existing medical conditions. The licensed medical professional (LMP) will consider adverse events serious if the event: (1) is life threatening, (2) results in death, (3) leads to incapacity, hospitalization, or serious impairment of normal life, (4) congenital abnormality or birth defect. Serious AEs will be reported to the IRB within 24 hours of the site becoming aware of the event. Once an adverse or serious adverse event is identified, it must be followed and recorded, such that subsequent to the designation each event

outcome should be characterized as follows: 1 = Still present, 2 = Resolved with Sequelae, 3 = Resolved without Sequelae, 4 = Lost to follow-up/Unknown, 5 = Death.

Determination of Severity. The study coordinators will make a determination of AE severity and provide a grade for each event according to the following criterion: Mild: Symptoms cause little discomfort, are easily tolerated, and do not significantly interfere with normal everyday activities. Moderate: Symptoms are uncomfortable and interfere with normal everyday activities. Severe: Symptoms cause significant impairment of everyday activities, incapacitation, or death

Determination of Causality. The LMP will make a determination the causality of each adverse event in relation to the study medication using the following criteria: 1 = Definite, 2 = Probable, 3 = Possible, 4 = Remote, 5 = Definitely Not

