Process for Handling AEs. At each visit and post-cessation call (and via EMA, see sub-study below), every participant will be asked to report on health status and adverse events. In addition, study participants will be instructed verbally and in writing to contact the study staff immediately if any health problem causes disruption in the participant's life — though participants will be informed to call 911 if they are experiencing any potentially life-threatening problems. Calls to the study staff will be triaged to determine if the study LMP should be contacted. The Arizona State University and LACT study physicians will address any medical problems that might arise (including working with each participant's health care provider if needed).

AE Reporting Period. All events not resolved or unrecovered by week 13 will be followed for 30 days after that date to assess status. Any participants lost to follow-up after a reported AE or serious AE will have 'unknown' indicated for that event.

Participant Payment

Main Study and Sub-studies. Note that all study participants will receive compensation for time and/or travel to the study sites as well as completing telephone visits during the treatment and follow-up study phases. Participants in the in-person cohort will be paid \$50 compensation for the screening/baseline visit, \$25 compensation for completing each of the weeks 2 and 13 telephone visits, \$50 for completing the in-clinic visits at weeks 4 and 8, and \$100 for completing the in-clinic week 12 visit (total of \$250), regardless of their smoking status. In addition, study participants will be compensated \$50 to come into the study sites to complete electronic questionnaires and to provide a breath CO if they report 7-day point prevalence abstinence at the 6-month follow-up call. Given the attrition that occurs in many smoking cessation studies, especially those that assess OTC medications, compensation for key study visits is essential.

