However, we will monitor very carefully the screening and ongoing participation of all participants. Study participants will only be allowed to participate and receive medication if the study licensed healthcare provider at each site has approved their participation after reviewing screening documents. Regular visits as well as assessments between visits will provide updates on potential adverse events, and any serious events will be assessed (including for causality) by the study physicians and reported to Western IRB and the study sponsor (National Institute on Drug Abuse/NIH) within 24 hours.

We will also identify an independent safety-monitoring panel (comprised of an MD and two additional scientists to be determined) who receive reports once a year on participant safety, protocol violations, medication use, and any other relevant topics in order to assure patient safety and study integrity. The safety-monitoring panel will assess all adverse events, and will make an independent recommendation on how study staff should address any concerns that they have raised. Their report will be maintained in the study file notebook.

E. DATA MANAGEMENT AND ANALYSIS

Data Collection, Management and Storage. All participant data will be collected and stored on the password protected iPad, and all iPads will be maintained in accordance with Good Clinical Practices and FDA regulations, e.g. in locked cabinets in locked rooms with acess restricted only to study personnel. Once each month, data will be securely sent from LA Clinical Trials to the Arizona State University, where the data will be stored for analysis. We are currently implementing a different study together, and the data transfer has worked well.

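### The independent safety panel is scheduled to hear once a year and is not named on the 24-hour serious-event notice; with 12-week dosing, about 77% of participants would finish drug before its next report if enrolment is steady.

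*Combined protocol and SAP*

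**What the plan says.** The Data Safety Monitoring Plan (section D, Participant Safety) describes an independent panel of one physician and two scientists, still to be chosen, "who receive reports once a year on participant safety, protocol violations, medication use, and any other relevant topics in order to assure patient safety". Its task is broad: "The safety-monitoring panel will assess all adverse events, and will make an independent recommendation". No timing is attached to that task other than the yearly report.

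Serious events follow a faster route that does not mention the panel. Section D has them assessed by the study physicians and "reported to Western IRB and the study sponsor (National Institute on Drug Abuse/NIH) within 24 hours". The adverse event definitions in section C name the IRB alone: "Serious AEs will be reported to the IRB within 24 hours of the site becoming aware of the event".

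The exposure period is short. Under Product Education Information: "Note that participants in all study conditions will have product available for a maximum of 12 weeks".

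**The concern.** The panel's only scheduled source of information arrives at intervals more than four times as long as the dosing period (52/12 = 4.3). The protocol gives the panel a remit over all adverse events, and safety is part of both primary objectives. If the panel learned of a serious event only from the annual report, its recommendation would usually be too late for the people who were taking study drug when the event happened. It could still help later enrollees, but the plan would lose much of the value of having an independent panel look at a signal promptly.

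**Working it through.** The documents give no figure for exposure between panel reports, so there is nothing of the plan's own to reproduce. They also give no accrual calendar, and the Recruitment section notes that "The COVID-19 pandemic has resulted in a drop in the number of potential participants contacting both sites in response to recruitment advertisements". Steady enrolment is therefore an assumption.

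**Inputs.** Report interval 52 weeks (section D). Dosing 12 weeks, or 84 days (Product Education Information). Contact days 14, 28, 52 and 98 (Table 2, Visit Window).

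**1. Share finishing dosing before the next report.** If entry is uniform over the reporting year, a participant with dosing length L finishes first with probability 1 - L/52.
- 12 weeks of dosing: 1 - 12/52 = 76.9%, or about 332 of 432.
- Remote supply of 1 ramp-up week plus 12 maintenance weeks, all used: 1 - 13/52 = 75.0%.
- End of dosing taken as the day-98 visit: 1 - 14/52 = 73.1%.
- Dosing starting 30 days after entry: 1 - (84 + 30)/365 = 68.8%.
- Enrolment ending part-way through a reporting year raises the share. For 1.75 years it is (0.770 + 0.75)/1.75 = 86.9%.

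If the rate is not steady, keeping 12 weeks of dosing, the share is (40/52)² = 59% for a rate rising linearly from zero over each reporting year and 1 - (12/52)² = 95% for the mirror-image fall.

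**2. Wait for the annual report.** For an event equally likely on any day of the year, the mean wait from site awareness is 52/2 = 26 weeks.

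**3. Others still on drug at that report.** Under steady enrolment, other participants on drug at the event have on average 84/2 = 42 days left. If the site is told at once, the share still on drug at the report is 42/364 = 12%. If the site learns only at the next scheduled contact, simulation gives 8%. Across the rising and falling patterns the range is 1% to 26%.

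**4. Delay before the site knows.** Participants are "instructed verbally and in writing to contact the study staff immediately if any health problem causes disruption", so the delay may be short. If nobody calls, it runs to the next contact. For an event uniform over days 0 to 84:
- Table 2 target days: 7 × 28/84 + 12 × 24/84 + 30 × 32/84 = 17.2 days on average.
- Nominal weeks (days 14, 28, 56, 84), since Table 2's days 52 and 98 are not 8 and 12 weeks: 7 × 28/84 + 14 × 56/84 = 980/84 = 11.7 days.
- Longest gap within the allowed windows: day 47 (Week 8) to day 103 (Week 12) = 56 days. Visits outside the windows are also permitted, so it can be longer.

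**5. With the copied notice.** The panel hears about 1 day after site awareness. The share of others still on drug when it advises depends on its time to convene, which is not stated. The table assumes steady enrolment and gives two illustrative values.

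| Site learns by | Advice on receipt | Advice 4 weeks later |
|---|---|---|
| Immediate call | 1 - 1/84 = 99% | 1 - 29/84 = 65% |
| Next contact, nominal days | 1 - 12.7/84 = 85% | 1 - 40.7/84 = 52% |
| Next contact, Table 2 days | 1 - 18.2/84 = 78% | 1 - 46.2/84 = 45% |

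**The case against.** The strongest reply is that this is a preference about oversight, not a defect. Study physicians assess every serious event, including causality. The IRB and the sponsor hear within 24 hours, and calls are triaged. Section D also explains why lighter panel oversight might be enough: the drug is approved and used at or below its approved dose, and serious drug-related events are judged very unlikely. The copied notice would show the panel only what the IRB and sponsor already see. All of this stands, and it is why the point is optional.

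It is also fair that the sentence giving the panel its remit is separate from the annual-report sentence and carries no timing, and that an unconstituted panel may yet write its own procedures. A reader might infer that the protocol bars the panel from acting between reports. It does not; it simply does not provide for it. If earlier contact is intended, one sentence would say so.

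The 77% describes the fit of the annual schedule. It does not measure the benefit of the fix, which leaves that figure unchanged. The benefit is the earlier notice, and it shrinks as the panel takes longer to convene: in the slowest row of the table, fewer than half of the others are still on drug when the advice arrives.

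**Conclusion.** The point holds as a cheap improvement. On the written schedule, about 77% of participants finish dosing before the panel's next report. This assumes steady enrolment over whole reporting years, with entry and first dose together. The range is about 69% to 87% under the other steady-rate readings, and 59% to 95% if the rate rises or falls linearly. Advice based only on the annual report would reach a minority of those on drug at the time of a serious event, at most about 26% in the patterns tried.

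The gain from the fix is that the panel is informed about 1 day after site awareness instead of a mean of about 26 weeks. Site awareness may itself lag the event by about 12 to 17 days on average if nobody calls, and by 56 days or more at worst.

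A reader might go further and infer that participants are unprotected, that a given harm would be averted, or that a stopping rule is needed. The documents support none of these. Physician, IRB and sponsor oversight is in place, and no serious-event rate is given from which an avoided harm could be estimated.

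**What to change.** Add one sentence to section D, Participant Safety: *Each serious adverse event report will be copied to the safety-monitoring panel, without treatment-arm information, on the existing 24-hour notice to the IRB and sponsor (counted from site awareness), and the panel may convene an unscheduled review on receipt.* Keep the annual report as it is.

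The cost is small. At an assumed serious-event frequency of 0.5% to 3% of 432 participants, it means about 2 to 13 extra emails over the trial (432 × 0.005 = 2.2; 432 × 0.03 = 13.0) and possibly an occasional unscheduled call. Blinding is unaffected. No new committee, visit, form, analysis or stopping rule is needed.
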